**List of warnings and cautions:**

Any patient with unexplained severe hemolysis, hemoglobinemia, and renal failure with increase in creatinine should be evaluated for hemolytic uremic syndrome (HUS). Oxaliplatin should be held in the event of hemolysis with renal failure until its etiology is determined in order to exclude the potential for HUS. Oxaliplatin should not be restarted if there is HUS. Evaluation for HUS should include CBC, differential, platelets, PT, PTT, fibrinogen, FDP, AT III, VWF, ANA, C3, C4, CH50, anti-platelet antibody, platelet-associated IgG, and circulating immune complexes. Renal evaluation should include creatinine, BUN, and urinalysis.

## 7.4 Leucovorin

### 7.4.1 Other Names:

Leucovorin, Wellcovorin, Citrovorum factor, folinic acid, 5formyltetrahydrofolate, LCV

### 7.4.2 Classification

Tetrahydrofolic acid derivative

### 7.4.3 Mode of Action

Leucovorin acts as a biochemical cofactor for 1-carbon transfer reactions in the synthesis of purines and pyrimidines. Leucovorin does not require the enzyme dihydrofolate reductase (DHFR) for conversion to tetrahydrofolic acid. The effects of methotrexate and other DHFR-antagonists are inhibited by leucovorin. Leucovorin can potentiate the cytotoxic effects of fluorinated pyrimidines (i.e., fluorouracil and floxuridine). After 5-FU is activated within the cell, it is accompanied by a folate cofactor, and inhibits the enzyme thymidilate synthetase, thus inhibiting pyrimidine synthesis. Leucovorin increases the folate pool, thereby increasing the binding of folate cofactor and active 5-FU with thymidilate synthetase.

### 7.4.4 Storage and Stability

All dosage forms are stored at room temperature. The reconstituted parenteral solution, 10 mg/mL, is stable for at least 7 days at room temperature. At concentrations of 0.5-0.9 mg/mL the drug is chemically stable for at least 24 hours at room temperature under normal laboratory light. The oral solution, 1 mg/mL, is stable for 14 days refrigerated and 7 days at room temperature.

### 7.4.5 Dose Specifics

400 mg/m^2 diluted in 250 cc of D5W. Leucovorin is only compatible with D5W and is administered as a 2-hour infusion on day 1 of each 2 week cycle.

### 7.4.6 Preparation

The 50 and 100 mg vials for injection are reconstituted with 5 and 10 mL of sterile water or bacteriostatic water, respectively, resulting in a 10 mg/mL solution. The 350 mg vial is reconstituted with 17 mL of sterile water resulting in a 20 mg/mL solution.

	60 seconds	30 seconds
--	------------	------------

The 60 mg bottle for oral solution is reconstituted with 60 mL of aromatic elixir provided, resulting in a 1 mg/mL oral solution

#### 7.4.7 Administration

Leucovorin will be given as an intravenous infusion over 2 hours.

#### 7.4.8 Compatibilities

Leucovorin (0.5-0.9 mg/mL) is chemically stable for at least 24 hours in normal saline, 5% dextrose, 10% dextrose, Ringer's injection or lactated Ringer's injection.

Leucovorin (0.03, 0.24 and 0.96 mg/mL) is stable for 48 hours at room and refrigeration temperatures when admixed with floxuridine (FUDR, 1, 2 and 4 mg/mL)

in normal saline. Leucovorin is also compatible with fluorouracil.

#### 7.4.9 Availability

Commercially available as a tablet (5, 10, 15, 25 mg), cryodesiccated powder for oral solution, and in parenteral formulations (3 and 5 mg ampule; 50 mg, 100 mg and 350 mg vial). Supply for this clinical trial will be commercial.

#### 7.4.10 Side Effects

Dermatologic: Skin rash.

Gastrointestinal: Nausea, upset stomach, diarrhea.

Allergic: Skin rash, hives, pruritus.

Pulmonary: Wheezing (possibly allergic in origin).

Other: Headache; may potentiate the toxic effects of fluoropyrimidine therapy, resulting in increased hematologic and gastrointestinal (diarrhea, stomatitis) adverse effects.

#### 7.4.11 Nursing Implications

Observe for sensitization reactions.

When given with fluoropyrimidines monitor closely for diarrhea and stomatitis.

## 8. STUDY CALENDAR

**Schedules shown in the Study Calendar below are provided as an example and should be modified as appropriate.**

Baseline history, physical and blood work are to be conducted within 2 weeks prior to start of protocol therapy. Scans and x-rays must be done  $\leq 4$  weeks prior to the start of therapy. Laboratory evaluations should be repeated within 24 hours prior to initiation of the next cycle of therapy. [ Cycle 1 refers to week of first actual therapy with mFOLFIRINOX.]

	Pre-Study	Cycle 1	Cycle 2	Cycle 3	Cycle 4	Week +4 weeks after Cycle 4 completion	Week +4-6 After Cycle 4 completion	Cycle 5 e	Cycle 6	Cycle 7	Cycle 8	Week +4 after completion of Cycle 8	Off Study d
Informed consent	X												
Demographics	X												
Medical history	X		X	X	X	X		X	X	X	X	X	X
Toxicity Assessment			X	X	X	X			X	X	X	X	
Physical exam	X		X	X	X	X		X	X	X	X	X	X
Vital signs	X	X	X	X	X	X		X	X	X	X	X	X
Height	X												
Weight	X	X	X	X	X	X		X	X	X	X	X	X
Performance status	X	X	X	X	X	X		X	X	X	X	X	X
CBC w/diff, plts	X		X	X	X	X		X	X	X	X	X	X
Serum chemistry a	X		X	X	X	X		X	X	X	X	X	X
Pregnancy test b	X							X					
CA 19-9	X			X		X		X		X		X	X
Radiologic evaluation c	X					X		X				X	
Chemotherapy		X	X	X	X			X	X	X	X		
Surgery							Exact timing per surgeon						

- a. Specific minimal lab tests required –Na, K, Mg, Phosphorus, Glucose, BUN,CO2, Chloride Creatinine, Calcium, Total Protein, Albumin, Total Bilirubin, Alkaline Phosphatase, SGOT, SGPT      b. May be serum or urine.
- c. CT scan of chest/abdomen/pelvis **or** MRI of abdomen/pelvis plus CXR if CT scan cannot be done.
- d. Follow up visits and studies per usual standard of care but not less than every 3 months for years 1-2 and every 6 months for years 3-5.
- e. Cycle 5 starts 4-10 weeks after surgery depending on patient recovery

## 9. MEASUREMENT OF EFFECT

### 9.1 Antitumor Effect

For the purposes of this study, RECIST 1.1 will be used. Patients should initially be re-evaluated for response 4 weeks after completion of 4 cycles of chemotherapy. Response and progression will be assessed in this study by evaluation at GI tumor board, with the presence of a minimum of one hepatobiliary surgeon, one medical oncologist and one radiologist. Should this not be possible, then an ad hoc meeting of these individuals should be convened forthwith for the purposes of making this determination.

If patients are not deemed resectable after the initial phase of chemotherapy, then the patient is off study and therapy will proceed at the discretion of the treating physicians.

#### 9.1.1 Definitions

Evaluable for toxicity. All patients will be evaluable for toxicity from the time of their first treatment.

Evaluable for objective response. All patients included in the study must be assessed for response to treatment, even if there are major protocol treatment deviations or if they are ineligible. These patients will have their response classified according to the definitions stated in Section 12.6.2

#### 9.1.2 Disease Parameters

Measurable disease. Measurable lesions are defined as those that can be accurately measured in at least one dimension (longest diameter to be recorded)  $\geq 10$  mm with CT scan. All tumor measurements must be recorded in millimeters (or decimal fractions of centimeters).

Malignant lymph nodes. To be considered pathologically enlarged and measurable, a lymph node must be  $\geq 15$  mm in short axis when assessed by CT scan (CT scan slice thickness recommended to be no greater than 5 mm). At baseline and in follow-up, only the short axis will be measured and followed.

Non-measurable disease. All other lesions (or sites of disease), including small lesions (longest diameter  $< 10$  mm or pathological lymph nodes with  $\geq 10$  to  $< 15$  mm short axis), are considered non-measurable disease and will exclude the patient from participation in this protocol.

Note: Cystic lesions that meet the criteria for radiographically defined simple cysts should not be considered as malignant lesions (neither measurable nor non-measurable) since they are, by definition, simple cysts.

Target lesions. The only target lesion relevant to this study is the pancreatic primary and any additional disease will render the patient ineligible for this study.

Non-target lesions. These are not permissible on this study.

### 9.1.3 Methods for Evaluation of Measurable Disease

All measurements should be taken and recorded in metric notation using a ruler or calipers. All baseline evaluations should be performed as closely as possible to the beginning of treatment and never more than 4 weeks before the beginning of the treatment.

The same method of assessment and the same technique should be used to characterize each identified and reported lesion at baseline and during follow-up. Imaging-based evaluation is the only permitted method for this study.

Conventional CT and MRI This guideline has defined measurability of lesions on CT scan based on the assumption that CT slice thickness is 5 mm or less. If CT scans have slice thickness greater than 5 mm, the minimum size for a measurable lesion should be twice the slice thickness. MRI is also acceptable as a substitute.

PET-CT At present, the low dose or attenuation correction CT portion of a combined PET-CT is not always of optimal diagnostic CT quality for use with RECIST measurements. However, if the site can document that the CT performed as part of a PET-CT is of identical diagnostic quality to a diagnostic CT (with IV and oral contrast), then the CT portion of the PET-CT can be used for RECIST measurements and can be used interchangeably with conventional CT in accurately measuring cancer lesions over time. Note, however, that the PET portion of the CT introduces additional data which may bias an investigator if it is not routinely or serially performed. The use of PET-CT is discouraged in this study.

Ultrasound Ultrasound is not useful in assessment of lesion size and should not be used as a method of measurement. Ultrasound examinations cannot be reproduced in their entirety for independent review at a later date and, because they are operator dependent, it cannot be guaranteed that the same technique and measurements will be taken from one assessment to the next. If new lesions are identified by ultrasound in the course of the study, confirmation by CT is advised.

Endoscopy, Laparoscopy The utilization of these techniques for objective tumor evaluation is not advised. However, such techniques may be useful to confirm complete pathological response when biopsies are obtained or to determine relapse in trials where recurrence following complete response (CR) or surgical resection is an endpoint.

Tumor markers Tumor markers alone cannot be used to assess response. If markers are initially above the upper normal limit, they must normalize for a patient to be considered in complete clinical response.

Cytology, Histology These techniques can be used to differentiate between partial responses (PR) and complete responses (CR) in rare cases (e.g., residual lesions in tumor types, such as germ cell tumors, where known residual benign tumors can remain).

The cytological confirmation of the neoplastic origin of any effusion that appears or worsens during treatment when the measurable tumor has met criteria for response or stable disease is mandatory to differentiate between response or stable disease (an effusion may be a side effect of the treatment) and progressive disease.

FDG-PET: This test is neither required nor encouraged for this study.

#### 9.1.4 Response Criteria

This study is unique in that the response evaluation is geared towards the maintenance of resectable status, no evidence of locally progressive or metastatic disease, and ultimately undergoing a resection.

##### 9.1.4.1 **Tumors considered resectable according to current NCCN guidelines include the following:**

- a. No distant metastases.
- b. No radiographic evidence of superior mesenteric vein (SMV) and portal vein abutment, distortion, tumor thrombus, or venous encasement.
- c. Clear fat planes around the celiac axis, hepatic artery, and superior mesenteric artery (SMA).

##### 9.1.5 Progression-Free Survival (PFS)

PFS is defined as the duration of time from start of treatment to time of progression or death, whichever occurs first.

##### 9.1.6 Overall Survival (OS)

OS is defined as the duration of time from start of treatment to time of death from any cause.

## 10. DATA REPORTING / REGULATORY REQUIREMENTS

Adverse event lists, guidelines, and instructions for AE reporting can be found in Section 6.0 (Adverse Events: List and Reporting Requirements).

## 10.1 Data Reporting

### 10.1.1 Method

**Note:** All adverse events that have occurred on the study must be reported via the monitoring method identified above.

#### 11.1.2.1 Responsibility for Data Submission

Study participants are responsible for submitting data and/or data forms to the Coordinating Center *within 2 weeks of each cycle along with source documentation for CRFs* to allow time for Coordinating Center compilation, and Principal Investigator review.

## 11.0 STATISTICAL CONSIDERATIONS

### 11.1 **Study Design/Endpoint(s).**

#### 12.1.1 Primary Endpoint

To evaluate the percentage of patients able to complete the full course of preoperative chemotherapy and undergo a resection. This will be the primary determinant of success for this pilot study.

Early withdrawals due to toxicity, disease progression, or intercurrent illness will be considered failures.

#### 11.1.2 Secondary Endpoints

11.1.2.1 To evaluate the percentage of patients able to complete the full course of therapy, including preoperative chemotherapy, surgical resection and postoperative chemotherapy.

11.1.2.2 To assess treatment related toxicity and other adverse events (AEs) during preoperative and postoperative therapy and the safety of this approach.

11.1.2.3 To assess the R0 resection rate.

11.1.2.4 To determine progression-free survival and overall survival from the start of study treatment.

## 11.2 **Stratification factors.**

Not applicable.

## 11.3 **Sample size with power justification.**

This pilot study will be conducted using a minimax two-stage design to test the null hypothesis that the success rate is 50% or less versus the alternative that it is at least 75%. Nine patients are to be enrolled in the first stage. If four or fewer patients meet the criteria for success, the trial would be terminated. Otherwise, an additional twelve patients (for a total of 21) are to be enrolled, and if fourteen or more successes are observed then the regimen will be considered worthy of additional evaluation in this disease. This design yields at least 0.85 probability of a positive result if the true success rate is at least 75% and at least 0.90 probability of a negative result if the true success rate is at most 50%.

## 11.4 **Plans for analysis including plans for formal interim analysis.**

The proportion of patients completing preoperative therapy and undergoing resection will be calculated, and a confidence interval constructed based on the binomial distribution. Progression-free and overall survival will be calculated by using the method of Kaplan and Meier. The frequency of various AEs (worst grade) will be tabulated.

Because surgery-related deaths are of concern after administration of FOLFIRINOX, there will be close monitoring of this adverse event. Specifically, a stopping rule developed by Goldman will be used as a guide for early termination due to surgery-related deaths. The trial may be halted if there is evidence that the true mortality rate is increased from an acceptable level of 3% to an upper limit of 10% assuming an alpha level of 5% and power of 80%. The stopping rule requires that early termination be considered if 3 deaths occur in the first 14 or fewer patients or four deaths in the first 31 or fewer patients. Additionally, febrile neutropenia, platelet counts less than 20,000, and diarrhea requiring hospitalization are also of concern. A stopping rule, based on an acceptable level of 10% and upper limit of 20%, requires that early termination be considered if 4 such adverse events occur in the first 4 patients, 5 such adverse events occur in the first 10 or fewer patients, 6 such adverse events in the first 17 or fewer patients, or 7 such adverse events in the first 24 or fewer patients. Delayed time to surgery and delayed wound healing are also of concern and will be reported and tabulated carefully. In order to monitor these events very closely, there will be a weekly telephone call between site PI's, and any events of concern will be immediately disseminated for discussion by all investigators. A monthly report will be generated for distribution to all investigators to update the group on the status of the study and of the patients on the study. Any concerns will receive immediate attention by the PI's.

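### The surgery-death stopping guide is stated with 5% alpha and 80% power, but with at most 21 patients it signals in only about 21% of trials at 10% mortality, and attained figures are not given

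*Combined protocol and SAP*

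**What the plan says.** Section 11.4 names surgery-related deaths as a concern and says that a published sequential rule "will be used as a guide for early termination due to surgery-related deaths". The trial may be halted on evidence that mortality has risen "from an acceptable level of 3% to an upper limit of 10% assuming an alpha level of 5% and power of 80" percent. Early termination is to be considered if "3 deaths occur in the first 14 or fewer patients or four deaths in the first 31 or fewer patients".

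Section 11.3 fixes the size of the trial. Nine patients enter stage 1, and the trial ends there with 4 or fewer successes. If it goes on to stage 2, "an additional twelve patients (for a total of 21) are to be enrolled". The primary rule comes with attained probabilities, starting "This design yields at least 0.85 probability of a positive result". Section 11.4 gives no corresponding figures for the surgery-death guide and does not say whether its count runs over enrolled or operated patients.

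**The concern.** The second limit runs to patient 31, ten beyond the largest possible trial, so the 5% and 80% cannot have been worked out for this sample size. Coming straight after a section that reports attained probabilities, the 80% is easily read the same way: that a true surgical mortality of 10% would trigger the guide in about four trials out of five.

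This is the plan's only numerical limit for surgery-related deaths. If the real chance of a signal is far lower, investigators and oversight bodies could take the absence of a signal as reassurance that it does not provide.

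**Working it through.** **Inputs.** From Section 11.4: acceptable mortality 3%, upper limit 10%, alpha 5%, power 80%; stop at 3 deaths for n ≤ 14 and at 4 deaths for n = 15 to 31. From Section 11.3: at most 21 patients; stop after 9 if 4 or fewer are successes.

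**Step 1: where the printed limits come from.** The upper line of a Wald sequential probability ratio test is crossed when

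d × ln(0.10/0.03) + (n − d) × ln(0.90/0.97) ≥ ln(0.80/0.05),

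that is, 1.2040 d − 0.0749 (n − d) ≥ 2.7726. Solving for n gives n ≤ (1.2789 d − 2.7726)/0.0749:

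- d = 3: n ≤ 14.2, so 3 deaths up to patient 14
- d = 4: n ≤ 31.3, so 4 deaths up to patient 31

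Both printed limits are reproduced. The 5% and 80% are therefore best read as inputs to this line.

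**Step 2: what the limits attain with 21 counted.** A crossing occurs either with 3 or more deaths in the first 14, or with fewer than 3 by then and a total of 4 reached in the next 7. With X14 and X7 independent binomial counts, at 10% mortality:

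- P(X14 ≥ 3) = 0.1584
- P(X14 = 2) × P(X7 ≥ 2) = 0.2570 × 0.1497 = 0.0385
- P(X14 = 1) × P(X7 ≥ 3) = 0.3559 × 0.0257 = 0.0091
- P(X14 = 0) × P(X7 ≥ 4) = 0.2288 × 0.0027 = 0.0006

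The sum is 0.2066. The same calculation at 3% gives 0.0089.

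**Step 3: other counts.** Exact recursion after each counted patient:

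| Patients counted | Crossing at 3% | Crossing at 10% |
|---|---|---|
| 9 | 0.2% | 5.3% |
| 14 | 0.8% | 15.8% |
| 16 | 0.8% | 16.1% |
| 18 | 0.8% | 17.3% |
| 21 | 0.9% | 20.7% |
| 31 | 1.8% | 39.5% |

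Fourteen is the fewest resected patients in a positive trial, because "if fourteen or more successes are observed then the regimen will be considered worthy of additional evaluation in this disease" and a success must "complete the full course of preoperative chemotherapy and undergo a resection". Sixteen is 75% of 21, rounded (15.75).

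**Step 4: allowing for the stage-1 stop.** The probability of stopping at 9 patients is 0.049 at a 75% success rate and 0.500 at 50%. Assume that every resected patient is a success and that death is independent of success status. Crossing at 3% / 10% mortality is then:

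| Counting basis | 75% success | 50% success |
|---|---|---|
| All enrolled counted and at risk | 0.9% / 19.9% | 0.5% / 13.0% |
| Only resected counted | 0.7% / 15.3% | 0.2% / 5.4% |
| Enrolled counted, only resected at risk | 0.4% / 10.3% | 0.1% / 2.7% |

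**Step 5: what 80% would take.** In a full-length trial the guide is crossed with 80% probability only at a true mortality of about 23% (21 counted) or 28% (14 to 16 counted). If the Wald line is continued beyond the printed limits (5 deaths to 48, 6 to 65, 7 to 82, 8 to 99), crossing at 10% mortality is 79.5% at 90 patients and first reaches 80% at 92 (80.3%). That continuation is an assumption. Another one, holding the limit at 5 deaths from patient 32 on, reaches about 80% near 65 patients. Both are at least three times this trial's maximum.

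**The case against.** The strongest reply is that the plan writes of assuming 5% and 80%, which is the language of inputs, while Section 11.3 uses the language of results. On that view nothing is miscalculated and only the attained figures are missing. The reading of the wording is fair, and Step 1 supports it. But the power is printed without a horizon in a trial that cannot come near it, so the statement still misleads unless it is qualified.

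It can also be said that the rule is only a guide and that deaths get attention in other ways: expedited reporting of every grade 5 event (Section 6.4), monthly review (Section 4.3), and telephone calls and monthly reports (Section 11.4). Review therefore starts at the first death. This limits the practical harm. None of these routes, however, sets a number of deaths at which stopping is to be considered.

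The lower figures in Step 4 depend on who is at risk. Patients explored but not resected can also die of surgery, and a patient resected after an incomplete course would not be a success. Both could raise the resected-only figures, and those figures should be read with that reservation. The 20.7% does not depend on them.

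Finally, low power is inherent in a pilot of this size. At a single look at 21 patients, a cut-off of 2 or more deaths gives 13.0% / 63.5% and 3 or more gives 2.4% / 35.2% at 3% / 10% mortality, so no single cut-off meets 5% and 80%. That is true, and it is a reason not to print 80% without qualification.

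**Conclusion.** The point holds. The limits agree with their design inputs, but the stated 80% power is not attained: the guide is crossed with probability 20.7% at 10% mortality in a full-length trial with all 21 patients counted and at risk. That is the favourable case. Counting 14 to 18 patients gives about 16% to 17%, and the stage-1 stop reduces the figure further, by an amount that depends on the success rate and the undefined denominator. The false-alarm rate errs on the safe side, below 1% rather than 5%, so the material gap is power. At 10% mortality about four out of five full-length trials would give no signal. The full-length figures assume independent patients with a common mortality and a check after each counted patient. The point should be fixed, though the rule's advisory status and the case-by-case review of deaths moderate its effect.

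**What to change.** In Section 11.4, label the 5% and 80% as nominal inputs used to derive the boundary and say that they are not attained with at most 21 patients. Deleting them would also remove the misleading statement, but the derivation of the limits could then no longer be traced, so labelling is better.

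Add the attained crossing probabilities at 3% and 10% mortality for the trial's maximum size, stating the number counted and how the stage-1 stop is handled. State whether patients means enrolled or operated, and compute the figures on that basis. Note that within this trial the four-death limit can apply only from patient 15 to patient 21.

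The cost is protocol wording. The boundary, sample size, primary endpoint and decision rule stay as they are, and whether to adopt a different boundary is for the sponsor. The drawback is that the reported power will look much less favourable.
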